The overall goal of our proposed research is to implement a culturally-tailored community outreach and testing program to increase the reach, access, uptake, and impact of testing in Latinx communities in Oregon. This project will fully integrate with the NIH Rapid Acceleration of Diagnostics (RADx) consortium and its Coordination and Data Collection Center (CDCC). With guidance and leadership from our Latinx Community and Scientific Advisory Board, we will launch the proposed testing program which will result in 36 community testing sites to serve Latinx communities. For the proposed research activities, we will test the following questions:

- 1) Do culturally-informed interventions ('Promotores') increase test rates and health behaviors?
 - a. Community-level intervention to increase participation in testing: Evaluate whether 'Promotores de Salud,' a culturally-tailored outreach intervention that includes psychoeducation, information support, and motivational strategies to address barriers, results in more tests completed and more sites testing at full capacity, as compared to basic community-level outreach services.
 - b. Individual-level booster intervention to change future health behavior: Examine whether a brief, individual-level 'Promotores de Salud' intervention held during a testing event (compared to distribution of a pamphlet only) results in greater use of strategies that reduce transmission at the community and individual level. Individual moderators (e.g., substance use, perceived threat, health literacy, social determinants) will also be examined. We further hypothesize that this intervention will increase future test rates through repeat testing visits and

through ‘snowball’ recruitment of friends and family to attend future testing events.

C. Methods, Materials and Analysis

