## 4.3 Statistical Design and Power

### 4.3.a Optimization and Adaptive Research Design

The goal of this research approach is to test optimal strategies to increase SARS-CoV-2 testing in Latinx populations. The primary approach will be a sequential multiple armed randomized trial (SMART). The proposed SMART design will evaluate adaptive intervention strategies (AIS) which vary the testing delivery format and sequence of testing strategies tailored to Latinx communities. Our research will identify an optimal AIS at the site and individual level as well as explore downstream site and individual differences moderators for further personalization. Through the identification of an optimal AIS, our research will provide public health officials and health practitioners with data on specifically what is the most effective and efficient sequence and modal delivery of testing for underserved Latinx communities. Adaptive intervention strategies involve decision rules that specify how the type or intensity of a testing approach should change site response rates during the progress of implementation monitoring.

Moreover, our research design is a hybrid investigation combining effectiveness evaluation and implementation research to further understand what elements of implementation lead to sustainability of the optimal testing strategies. Because each AIS is designed to be a deliverable product for implementation, intervention approaches do not separately involve randomization. Rather, in the implementation of a SMART designed to evaluate these AISs, sites follow a two-stage randomization procedure in order to be assigned to each AIS. All sites are initially randomized to one of the two first-stage interventions. Sites are then re-randomized to one of the two second-stage intervention strategies. This randomization procedure allows an evaluation of the relative effectiveness of each overall AIS as well the ability to explore other questions such as which first-stage intervention is the most effective and which second-stage intervention format is the most effective for slow-responding sites. Unique analytic strategies are used to maximize power to address these questions within SMART designs (see Statistical Analysis Plan below).

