Within the SMART, a measure of initial response is assessed following implementation of the primary outreach approaches in order to evaluate each site's need for further adaptation. In this way, testing is tailored to meet the needs of communities and their Latinx individuals and families by providing enhanced testing strategies to slow-responding sites. This measure of initial response is referred to as a primary tailoring variable. In the proposed study, the primary tailoring variable is whether a site is operating at a threshold of 80% testing capacity, based on the frequency and per capita testing rates and presumption of 50 tests per testing event. The AIS each represent distinct plans of testing outreach approaches. Within the SMART, it is then possible to evaluate which adaptive sequence is the most effective in impacting Latinx testing rates and secondary outcomes such as health maintenance behaviors.

Specifically, the proposed RADx SMART includes 4 embedded adaptive intervention strategies (AIS). Sites and individuals in the proposed Latinx sampling frame will receive one of two first-stage implementation outreach strategies: Basic Outreach approaches or Basic Outreach plus Promotoras Comunitarias. Primary outcomes will be site level testing rates and individual level COVID-19-related health behaviors. After the initial 4 weeks (2 testing events), sites will be re-randomized in the second-stage randomization to either stay the course stationary events or to a mobilization intervention. Thus, for the primary criterion outcome of testing capacity, the SMART design includes 4 embedded site level adaptive intervention strategies (AIS): (1) starting with culturally adapted Basic Outreach, and staying the course; (2) starting with Basic Outreach followed by mobilization intervention; (3) starting with Basic Outreach plus Promotoras Comunitarias and staying the course; and (4) starting with Basic Outreach plus Promotoras Comunitarias plus mobilization intervention. In addition, as a booster to the Promotoras Comunitarias intervention, for health behavior outcomes, individuals tested at Basic Outreach sites will receive pamphlet health promotion pamphlets, and those tested at Promotoras Comunitarias sites, will receive a health pamphlet plus a Promotoras de Salud intervention.

[figure not shown]

Figure 4.3.1

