#### 4.3.b Embedded AIS Research Questions and Aims

The specific research questions and aims are the following. Question 1a: Is Basic Outreach plus Promotoras Comunitarias more effective for maximizing testing capacity than Basic Outreach? Question 1b: For individuals tested, is Pamphlet plus Promotoras de Salud more effective than Pamphlet only in supporting positive health behaviors for individuals tested? [(A+B+C+D) vs (E+F+G+H)]. Research Aim Question 2: Among slow responding sites, does the mobilization intervention yield an increase in individual positive health behaviors and in site testing capacity? [(D+H) vs (C+G)].

Each of these AIS research questions is depicted in Figures 4.3.2 through 4.3.3:

**Question 1a:** Is Basic Outreach plus Promotoras Comunitarias more effective for testing capacity than Basic Outreach alone, for Latinx communities?

**Question 1b:** For individuals tested, is Pamphlet plus Promotoras de Salud more effective than Pamphlet only in supporting positive health behaviors for individuals tested, and increasing site testing rates?

**Aim 1a:** Is Basic Outreach plus Promotoras Comunitarias more effective for testing capacity than Basic Outreach alone?

**Aim 1b:** For individuals tested, is Pamphlet plus Promotoras de Salud more effective than Pamphlet only in supporting positive health behaviors for individuals tested, and increasing testing rates?

[figure not shown]

Figure 4.3.2

**Research Aim Question 2:** Among slow responding sites, does the mobilization intervention yield an increase in site testing capacity?

**Aim 2:** Among slow responding sites, does the mobilization intervention yield increase in site testing capacity?

[figure not shown]

Figure 4.3.3

In addition to research questions 1 and 2, the SMART design also allows for an omnibus comparison; after starting with Basic Outreach or Basic Outreach + Promotoras Comunitarias, we can examine which of the embedded adaptive intervention strategies is more effective overall for testing capacity and health behavior maintenance [A vs B vs C vs D vs E vs F vs G vs H]. Although not a specific aim of the proposed study, agencies and stakeholders may be particularly interested in this question and our study design will allow us to test this, focusing on the combined R1 and R2 strategies.

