#### **4.3.d Data Analysis for Aims 1 and 2**

For the primary evaluation aims for determining the optimal strategy for testing Latinx communities and the four adaptive intervention strategies, we will employ standard normal theory generalized linear modeling analysis of covariance fractional factorial analyses using pre-post assessment scores for site and individual level outcomes. Research Question 1 will focus on the combined effects of A1 randomization groups [(A+B+C+D) vs (E+F+G+H)]. Research Question 2 will focus on which A2 strategy works best for slow-responding sites [(D+H) vs (C+G)]. To address the non-independence of subjects in the embedded adaptive intervention designs and crossed factors, we will estimate linear mixed models with weighted least squares using the design effects coding shown in Table 4.3.1.

The general equation to estimate the optimal strategy is given by

$$E[Y|A_1, A_2, O_1] = \beta_0 + \beta_1 A_1 + \beta_2 A_2 + \beta_3 A_1 A_2 + \gamma^T O_1$$

where  $E$  is the expected value of the outcome,  $A_1$  is the initial treatment randomization,  $A_2$  is the second stage treatment randomization and  $\gamma^T$  are the estimates for covariate  $O_1$ , the pre-test covariate. For binary and count data we will employ generalized linear modeling and logit, probit, and poisson link functions for criterion outcomes such as frequency of tests, re-tests, and discrete event behaviors.

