Finally, when considering power for individual level data, a mixed model with two levels (individuals nested within sites) we must consider full capacity scenarios where implementation is realized at full capacity (roughly 3600 tests) to scenarios that obtain a smaller number of individual tests based on response patterns by site. In this case, that is the balanced scenario shown in Figure 4.3.1 given half of the sites are slow responding. That scenario projects a maximum of 2520 level-1 testing units sampled from 36 sites and achieves .80 power to detect a difference of .22 (a small effect) among the group conditions for randomization 1 conditions A1, randomization 2 conditions A2, and their crossed A1A2 interaction, and an intraclass correlation of .05 for the test of comparative intervention strategies from the primary equation shown above. Thus, the study is adequately powered for all multilevel data scenarios for minimum response to maximum response to detect small effect sizes. Power for individual comparisons among the 4 embedded AISs is shown in Figure 4.3.f.

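### Aim 1b asks whether the individual booster beats a pamphlet, but the booster follows the first-stage site arm, so the randomized comparison tests only the whole promotores package

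*SAP*

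**What the plan says.** The protocol separates two questions. Section B, 1a concerns community-level outreach. Section B, 1b concerns an individual-level booster, asking whether a brief "intervention held during a testing event (compared to distribution of a pamphlet only) results in greater use of strategies" that reduce transmission. It adds a testing hypothesis for the same booster: "We further hypothesize that this intervention will increase future test rates through repeat testing visits and" through participants bringing in friends and family.

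SAP 4.3.b repeats the question and attaches a contrast to it: "is Pamphlet plus Promotoras de Salud more effective than Pamphlet only in supporting positive health behaviors for individuals tested? [(A+B+C+D) vs (E+F+G+H" (closing brackets omitted). The restated Question 1b in the same section widens the outcome: "in supporting positive health behaviors for individuals tested, and increasing site testing rates".

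The allocation is in SAP 4.3.a. People tested at Basic Outreach sites receive a pamphlet; "those tested at Promotoras Comunitarias sites, will receive a health pamphlet plus a Promotoras de Salud intervention". The same section says: "Because each AIS is designed to be a deliverable product for implementation, intervention approaches do not separately involve randomization". Protocol Section C puts randomization at site level, 18 sites per arm, and describes the promotores condition as outreach, direct educational contact and a pamphlet together.

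For the analysis, SAP 4.3.d says: "Research Question 1 will focus on the combined effects of A1 randomization groups [(A+B+C+D) vs (E+F+G+H". Its model has A1, A2, A1A2 and a pre-test covariate O1. The individual-level power in SAP 4.3.f is for differences "among the group conditions for randomization 1 conditions A1, randomization 2 conditions A2, and their crossed A1A2 interaction".

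**The concern.** Aim 1b is worded as a question about one component: what the on-site booster adds to a pamphlet. The design has no arm with outreach but no booster, and none with the booster but no outreach. People in the booster condition differ from the pamphlet-only group in two ways: they had the booster, and their community had promotores outreach beforehand.

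SAP 4.3.a names health behaviors as a primary outcome alongside site testing rates. If the A1 contrast on health behaviors is positive and is described in the words of Aim 1b, an agency could adopt the on-site booster alone on evidence that is equally compatible with outreach having done all the work. In addition, because the restated Question 1b includes site testing rates, a single A1 result on that outcome could be counted as support for both 1a and 1b.

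**Working it through.** The plan gives no figure for a booster effect, so there is none to reproduce. The .22 used below is the individual-level difference quoted in SAP 4.3.f, borrowed only as a scale. The argument does not depend on the power calculation behind it.

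**Step 1. Who gets what (SAP 4.3.a).**

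| First-stage arm | Sites | Promotores outreach | Booster | Pamphlet |
|---|---|---|---|---|
| Basic Outreach | 18 | no | no | yes |
| Basic Outreach plus Promotoras Comunitarias | 18 | yes | yes | yes |

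The outreach and booster columns are identical.

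**Step 2. Consequence for the model.** Let *o* be the outreach effect and *b* the booster effect. With A1 = 1 for promotores sites and 0 otherwise, the arm part of the mean is *o*·A1 + *b*·A1 = (*o* + *b*)·A1. Under any other two-level coding, the booster indicator is still an exact linear function of the intercept and A1. Checking the rank of the SAP 4.3.d model matrix, with 36 sites of 70 people (36 × 70 = 2,520, the SAP 4.3.f scenario):

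- Intercept, A1, A2, A1A2: rank 4. Adding a booster column gives 5 columns, still rank 4.
- With O1 as well: rank 5. Adding a booster column gives 6 columns, still rank 5.

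**Step 3. A1 contrast without O1.** The contrast equals *o* + *b*:

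- outreach .22, booster 0: .22 + 0 = .22
- outreach .11, booster .11: .11 + .11 = .22
- outreach 0, booster .22: 0 + .22 = .22

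The three cases cannot be told apart.

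**Step 4. A1 coefficient with O1, as planned.** For the health-behavior survey, the only earlier measure described is the survey taken at the testing event (Protocol Sections C and D), by which time outreach has begun. Suppose that outreach has already had its full effect at that survey, that the booster comes after it, and that the slope of follow-up on O1 is *s*. The adjusted coefficient is then (*o* + *b*) − *s*·*o* = *o*(1 − *s*) + *b*. With an assumed *s* = .5 (not in the documents), the three cases give:

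- .22 × .5 + 0 = .11
- .11 × .5 + .11 = .165
- 0 × .5 + .22 = .22

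So the equality in Step 3 does not carry over to the planned model. Under these assumptions O1 removes part of the outreach contribution.

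**Step 5. What leaving O1 out can do.** Respondents are people who came to an event and agreed to the survey, and outreach is meant to change who comes. Suppose there is no effect at all, but attendees differ between arms by .2 SD on O1, again with *s* = .5 (both assumed). The unadjusted contrast is then off by .5 × .2 = .10, and the adjusted one is near 0. Neither version is clearly preferable on what the documents say.

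**Step 6. Site testing rates.** Question 1a is the A1 contrast on testing at the site. The restated Question 1b, for its testing part, is the A1 contrast on site testing rates. It is one test with two labels. Repeat testing is different: Protocol Section B names it as a mechanism for the booster, and SAP 4.3.d lists re-tests separately from frequency of tests. The contrast is shared but the outcome is not.

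**The case against.** The strongest reply is that the package design is disclosed. The SAP says that approaches are not randomized separately, presents the booster as an addition to Promotoras Comunitarias, and describes Question 1 as a combined effect of the A1 groups. A trial of adaptive strategies compares strategies, and the absence of a booster term from the model and power statement is consistent with that. All of this stands, and it is why the fault lies in the wording of Aim 1b and not in the randomization. It does not remove the component question, which the protocol sets apart from 1a. Nor does any reporting text say that a booster claim will be made; that is a risk created by the aim as worded.

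Four stronger readings are tempting, and the documents do not support them:

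- *The data can say nothing about the booster.* If the event survey comes before the booster and the outreach effect is already present and stable, a change-from-event comparison would give 0, .11 and .22 in the three cases above. That rests on those assumptions and on comparable attendees, not on randomization, so it does not establish a booster effect. It does mean that the limit is on the randomized evidence.
- *The O1-adjusted model should be demoted.* The documents do not say whether the event survey comes before or after the booster, and Step 5 shows that O1 may correct differences in who attends. It is a trade-off.
- *Every testing outcome under 1b duplicates 1a.* This is true of site testing rates, not of repeat testing.
- *Protocol Section G rescues 1b.* It says that one in two participants at the intervention site would be offered the intervention. Read literally, that would create a within-site comparison. It may be loose wording for half of the whole sample, and neither document describes a within-site randomization or an analysis to go with it. It also does not fit SAP 4.3.a, or Protocol Section D's split of up to 1,800 survey respondents per condition.

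**Conclusion.** The point holds as a mismatch between a stated aim and the design. No randomized contrast described in either document isolates the booster. In the A1 contrast without O1, a difference of .22 is compatible with a booster contribution of none of it, half of it or all of it. For site testing rates, 1a and 1b are the same contrast on the same outcome.

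This rests on SAP 4.3.a being followed as written, with the booster tied to site arm. The figures showing cells A to H are not in the text available, but the wording of SAP 4.3.a, 4.3.b and 4.3.d settles allocation and contrast. The numbers in Steps 4 and 5 depend on an assumed slope and an assumed attendee difference; they show direction only.

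A reader might infer that the trial's main comparison is compromised. It is not: A1 is a valid randomized test of the promotores package against basic outreach. The change needed is to what the trial says it tests, and it should be made before results are reported.

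**What to change.** 1. In SAP 4.3.b and Protocol Section B (1b), reword the question along these lines: *Among people tested, does the combined promotores package (outreach, booster and pamphlet), compared with basic outreach and a pamphlet, increase positive health behaviors?* Make no booster-only claim. Report the site testing-rate result once, under 1a, as a package effect. Keep repeat testing as a distinct outcome, also labelled a package effect.
2. Keep the planned O1-adjusted model in SAP 4.3.d and report the A1 estimate without O1 beside it. State that the event survey is taken after outreach has begun, so O1 may absorb part of the package effect. State also that respondents are a group formed after randomization, so the unadjusted estimate may partly reflect who attended.
3. Reconcile the sentence in Protocol Section G about half of participants with Protocol Section D and SAP 4.3.a, so that the documents give one account of who is offered the intervention.

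The cost is wording changes in two documents, one extra model run on data already planned, and a narrower claim for Aim 1b. No new data are needed.

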#### 4.3.b Embedded AIS Research Questions and Aims

The specific research questions and aims are the following. Question 1a: Is Basic Outreach plus Promotoras Comunitarias more effective for maximizing testing capacity than Basic Outreach? Question 1b: For individuals tested, is Pamphlet plus Promotoras de Salud more effective than Pamphlet only in supporting positive health behaviors for individuals tested? [(A+B+C+D) vs (E+F+G+H)]. Research Aim Question 2: Among slow responding sites, does the mobilization intervention yield an increase in individual positive health behaviors and in site testing capacity? [(D+H) vs (C+G)].

Each of these AIS research questions is depicted in Figures 4.3.2 through 4.3.3:

**Question 1a:** Is Basic Outreach plus Promotoras Comunitarias more effective for testing capacity than Basic Outreach alone, for Latinx communities?

**Question 1b:** For individuals tested, is Pamphlet plus Promotoras de Salud more effective than Pamphlet only in supporting positive health behaviors for individuals tested, and increasing site testing rates?

**Aim 1a:** Is Basic Outreach plus Promotoras Comunitarias more effective for testing capacity than Basic Outreach alone?

**Aim 1b:** For individuals tested, is Pamphlet plus Promotoras de Salud more effective than Pamphlet only in supporting positive health behaviors for individuals tested, and increasing testing rates?

[figure not shown]

Figure 4.3.2

**Research Aim Question 2:** Among slow responding sites, does the mobilization intervention yield an increase in site testing capacity?

**Aim 2:** Among slow responding sites, does the mobilization intervention yield increase in site testing capacity?

[figure not shown]

Figure 4.3.3

In addition to research questions 1 and 2, the SMART design also allows for an omnibus comparison; after starting with Basic Outreach or Basic Outreach + Promotoras Comunitarias, we can examine which of the embedded adaptive intervention strategies is more effective overall for testing capacity and health behavior maintenance [A vs B vs C vs D vs E vs F vs G vs H]. Although not a specific aim of the proposed study, agencies and stakeholders may be particularly interested in this question and our study design will allow us to test this, focusing on the combined R1 and R2 strategies.

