Overall Study Design: We will partner with community organizations to administer SARS-CoV-2 tests at organized, planned testing events located in communities across Oregon. Sample collection will occur in counties across Oregon and we will collaborate with county public health agencies to determine sites. Samples will be collected using services as usual using a standardized intake form and standardized, EUA authorized sample collection approaches. Data used to evaluate the efficacy of interventions will involve de-identified participant data at the level of the testing site. This study is a randomized clinical trial to test whether ‘Promotores,’ community health workers who deliver culturally-informed set of outreach, education, and engagement interventions, will result in an increase in testing utilization and health behaviors in Latinx communities.

Randomization will occur at the site level such that 18 sites will be randomized to receive the Promotores intervention and 18 will be randomized to receive services as usual. Services as usual include outreach by county public health and community-based organizations (fliers, radio ads, social media, etc.). The promotores intervention includes targeted outreach to Latinx community members and educational direct interactions with participants and distribution of a pamphlet, with the goal of increasing health behaviors and encouraging additional/future testing. The UO will provide support to community-based organizations to employ and train these promotores to assist with recruitment. The promotores will include Spanish speakers, across cultural contexts, living and working in, and intricately connected to, the target community.

- **Outreach as usual description**
 - Basic outreach materials document (flyers, social media posts, radio announcements, etc.)
 - Flyer to promote health behaviors
 - These documents may be modified or not used at all by community stakeholders as they may have other documents they are already using for outreach and health education—these materials are intended to be used for counties who do not have existing or preferred materials
 - See 04c.Services as Usual Materials
- **Promotores intervention description**
 - Basic outreach and flyer to promote health behaviors plus the outlined outreach and health behaviors promotores approaches
 - Promotores training will be provided by the study team
 - See 4d. Promotores Training Outline

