- 2. Individual level survey data** will include participants who are (a) age 15 years and older; (b) attending an NIH-funded testing event. Exclusion criteria include: (a) individual is unable to understand Spanish or English or another language translated by a qualified translator at a 5th grade level (participants who cannot read will have the consent or assent form read to them); (b) individual discloses that they previously enrolled in the research project. We anticipate up to 3,600 adult individuals will provide survey data. Up to 1,800 individuals will be individuals who had received the promotores intervention and up to 1,800 will have received services as usual. Recruitment will occur at the testing site, by a study research assistant. A standardized recruitment script (see recruitment information document) will be used and will include eligibility questions. Participants will be compensated with a \$30 gift card for each survey they complete (one at baseline, one at one month follow-up for a total of \$60 in gift card renumeration available). To recruit participants, we will also add the following text to testing event flyers circulated by our community partners '\$30 gift cards available for those eligible to participate in a research survey.'
- 3. Anonymous participant interview** will be collected from a sub-set of randomly selected individuals at NIH-funded testing events who are age 18 years or older. We will invite approximately 15 individuals to participate in a brief anonymous interview (5-8 open-ended questions) with a study staff member at our testing events. Anonymous interview data will assist with informing the study about individual behaviors related to attending testing events. We will audio record these interviews for transcription. All audio recordings will be destroyed after transcription activities are complete. A standardized recruitment script will be used, which will provide information about the purpose of the interview and permission for audio recording. Individuals will be compensated with a \$15 gift card for completion of this interview. These anonymous interviews will not be used as research data, and are only to provide feedback on the testing events. This aspect of the study has now been completed.

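### Question 1b compares health behaviors among people who came for testing, while the randomized outreach is meant to change who comes; the pre-test score corrects only part of any resulting difference

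*SAP*

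**What the plan says.** Allocation is by site: "Randomization will occur at the site level such that 18 sites will be randomized to receive the Promotores intervention" (Protocol, section C). SAP 4.3.c randomizes 3 communities to each condition within each of 6 counties, stratified by county and rurality.

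The randomized arm is a bundle: "The promotores intervention includes targeted outreach to Latinx community members and educational direct interactions with participants and distribution of a pamphlet" (Protocol, section C). Protocol section B expects it to produce more completed tests, and expects the on-site part to bring friends and family to later events. The booster follows the site's first-stage arm: "those tested at Promotoras Comunitarias sites, will receive a health pamphlet plus a Promotoras de Salud intervention" (SAP 4.3.a).

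Question 1b is put only for people who were tested: "For individuals tested, is Pamphlet plus Promotoras de Salud more effective than Pamphlet only in supporting positive health behaviors for individuals tested" (SAP 4.3.b). SAP 4.3.d answers Question 1 with the contrast between the two first-stage arms.

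On timing, "Recruitment will occur at the testing site, by a study research assistant" (Protocol, section D), with a survey at baseline and another at one month. The analysis is ANCOVA "using pre-post assessment scores for site and individual level outcomes" (SAP 4.3.d). The only covariate named for the model there is the pre-test.

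**The concern.** Attendance is an outcome of the randomized intervention (Aim 1a), and it also decides who enters the 1b analysis. If outreach draws in people who would otherwise have stayed away, attendees in the two arms may differ before any on-site contact. If the extra attendees face more barriers, the Promotores arm can look worse although the intervention helps. If they are unusually motivated contacts of promotores, it can look better with no effect.

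The pre-test score is only a partial remedy. ANCOVA removes the part of a compositional difference that the pre-score predicts and leaves the rest. Because the pre-score is itself measured after outreach, it may already contain some real benefit of the outreach education, which ANCOVA would subtract. A positive or a null 1b result would therefore be hard to interpret, particularly as evidence on pamphlet plus booster against pamphlet alone.

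**Working it through.** **The plan's detectable difference.** SAP 4.3.f gives 2520 people, 36 sites, an intraclass correlation of .05, two-sided alpha .05 and power .80, and states .22.

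- People per site: 2520/36 = 70. Design effect: 1 + 69 × .05 = 4.45.
- Standard error with SD 1: 2 × √(4.45/2520) = .084.
- Detectable difference: (1.96 + .84) × .084 = .235 by the normal approximation, or .242 using t with 34 degrees of freedom. Power at .22 is .745 or .720.

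The stated .22 is therefore not quite reproduced. A pre-test explaining about 13% of variance (18% with t) would give it, but no such value is stated. This gap is separate from the present point; .22 serves below only as a yardstick.

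**Size of a selection effect.** The documents give none of the following inputs, so all three are assumed:

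- s, the share of Promotores attendees present only because of outreach;
- D, their difference in behavior in SD, taken as equal at baseline and follow-up;
- ρ, the pre-post correlation, equal to the ANCOVA slope when both SDs are the same.

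False difference with no intervention effect: s × D unadjusted, and s × D × (1 − ρ) after ANCOVA. Standard error after ANCOVA: .084 × √(1 − ρ²), supposing the pre-test explains the same share of variance between and within sites. False-positive rate for a remaining bias b: 1 − Φ(1.96 − b/SE) + Φ(−1.96 − b/SE).

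Main illustration, s = .30, D = .2 to .5, ρ = .5:

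- Unadjusted: .30 × .2 = .06 and .30 × .5 = .15.
- After ANCOVA: .06 × .5 = .03 and .15 × .5 = .075. Divided by .22, this is 14% and 34%.
- Standard error: .084 × √.75 = .073. The bias is .03/.073 = 0.4 and .075/.073 = 1.0 standard errors.
- False-positive rate: about 7% and 18%, against a nominal 5%.

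Wider range of assumptions:

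| s | D | Unadjusted | After ANCOVA (ρ = .6 to .4) | False-positive rate after ANCOVA |
|---|---|---|---|---|
| .1 | .25 | .025 | .010 to .015 | about 5% |
| .2 | .5 | .10 | .04 to .06 | 9% to 12% |
| .3 | .75 | .225 | .09 to .135 | 27% to 42% |

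**The opposite error.** If outreach had already improved behavior by an assumed .1 to .2 SD before the baseline survey, ANCOVA would remove ρ times that amount: .4 × .1 = .04 up to .6 × .2 = .12 SD of real effect.

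**A caution on s.** The value .30 equals 1 − 70/100, where 70 and 100 are the per-site numbers implied by SAP 4.3.f (2520/36 and 3600/36). Those are response scenarios for the whole trial, not an arm difference, and do not support the assumption. Nor is 100 the attendance: the Protocol expects 32,000 to 36,000 people tested, about 890 to 1,000 per site if spread evenly over 36. It is the survey quota, 3,600/36.

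**The case against.** The site contrast is randomized, within county and by rurality. A reader might infer that randomization gives 1b no protection at all. The documents do not support that: communities are balanced, and the contrast can be read as the effect of the package on whoever attends. Nor do they show that attendees must differ; outreach can raise numbers without changing the mix. What stands is that balance of communities does not guarantee balance of attendees, and nothing planned checks or adjusts for it beyond the pre-test.

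The bundling is deliberate, since SAP 4.3.a describes each strategy as a deliverable product whose components are not separately randomized, and 1b is already limited to people tested. Both are true. But the question is still worded as a booster-over-pamphlet effect, which the contrast does not isolate.

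The Protocol plans to compare the Latinx share of attendees with local population density, and the covariate term in SAP 4.3.d is written as a vector that could hold more. The comparison describes turnout and adjusts nothing; the text names only the pre-test for the vector.

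A reader might infer that the baseline survey follows the promotor talk. The terms baseline and pre-test suggest the opposite. However, no passage states the order, and Protocol section D describes the Promotores survey group as people already exposed to the intervention.

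Protocol section G says half of the participants at the intervention site will be offered the intervention. Read as within-site allocation, this would weaken the point. It conflicts with SAP 4.3.a, and the planned analysis compares site arms in any case.

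**Conclusion.** The concern holds as a risk of selection bias whose size and direction the documents do not allow one to determine. It rests on three facts in the text: allocation by site, outreach within the randomized arm, and recruitment at the event afterwards. It does not depend on any assumed number.

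Under the main illustrative assumptions, the planned analysis leaves .03 to .075 SD, or 14% to 34% of .22, with a false-positive rate of about 7% to 18%. Other assumptions run from negligible to serious. The unadjusted .06 to .15 SD (27% to 68% of .22) should not be taken as the size of the problem, because the plan prespecifies ANCOVA.

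The weight of the point depends partly on the outcome's status, which is unsettled. Protocol section C names only site-level testing rates as primary, while SAP 4.3.a calls health behaviors primary in one place and secondary in another. The change is worth making because it costs little and limits what 1b can claim.

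**What to change.** - **Model.** In the 1b analysis, add to the pre-test score individual characteristics that outreach cannot change: age, race, ethnicity and social determinants. Add the county and rurality strata, which SAP 4.3.c says the analysis should reflect but the 4.3.d equation omits. Take the individual items from the survey, because participants may refuse linkage to intake data (Protocol, section E). The Protocol says the survey collects demographics and plans to examine social determinants; confirm the exact items. Do not enter residence zip code as indicators: communities are defined by zip code or cluster, so these would largely duplicate site and hence arm.
- **Reporting.** Show attendee characteristics by arm. State the 1b conclusion as the effect of the whole Promotores package among people who came for testing, read next to the arm difference in attendance, and not as the effect of the booster over the pamphlet.
- **Order of steps.** Confirm in writing that the baseline survey precedes on-site promotor contact in both arms.
- **Allocation text.** Protocol section G and SAP 4.3.a disagree on who at an intervention site is offered the intervention; the passages must be reconciled.

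The cost is SAP wording, slightly more analysis work and a more cautious 1b claim. Randomization and sample size are unchanged. Adjustment will not remove differences in motivation, so some residual confounding remains.
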